7.3.1.4.2 Secondary Endpoints

- In subjects with CML-CP, the objectives will be to evaluate the:
 - Hematological responses: Proportion of subjects who achieve or maintain complete hematological response
 - Cytogenetic response: Proportion of subjects who achieve CCyR
 - Molecular responses: Proportion of subjects who achieve major molecular response (MMR)
- In subjects with CML-AP, or CML-BP, the objectives will be to evaluate the:
 - Cytogenetic responses: Proportion of subjects who achieve CCyR, PCyR,
 - Molecular responses: Proportion of subjects who achieve MMR

- In all subjects: Safety and tolerability in terms of incidence and severity of treatment emergent AEs
- In all subjects: Time to response, duration of response, PFS and OS

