7.3.2.2 Classification of CML subjects

Subjects will be classified as per the NCCN guidelines for Chronic Myeloid Leukaemia¹³ as follows

Table 7-2 Classification of Subjects with CML

| CML Phase | Criteria |
|-------------------|--|
| Chronic Phase | $< 15\%$ blasts in peripheral blood or bone marrow and $< 20\%$ basophils in peripheral blood and $< 30\%$ (blasts + promyelocytes) in peripheral blood or bone marrow and $> 100 \times 10^9$ platelets/L in peripheral blood and No extra-medullary disease |
| Accelerated Phase | $\geq 15 - < 30\%$ blasts in peripheral blood or bone marrow or $\geq 20\%$ basophils in peripheral blood or bone marrow or $\geq 30\%$ (blasts + promyelocytes) in peripheral blood or bone marrow (but $< 30\%$ blasts) or $\leq 100 \times 10^9$ platelets/L in peripheral blood unrelated to therapy or Additional clonal cytogenetic abnormalities in Ph+ cells |
| Blast Crisis | $\geq 30\%$ blasts in peripheral blood, bone marrow or both or Extra-medullary disease |

Note: For subjects wherein rapid disease progression is observed (beyond the aforementioned criteria) and subject safety is a concern, the subject can be discontinued at Investigator's discretion in consultation with Sponsor or Sponsor nominated CRO's medical monitor.

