7.3.2.3 Criteria for Disease Progression

Table 7-3 Criteria for disease progression of subjects enrolled into the study

| Disease status at enrolment | Disease progression criteria | Reference |
|-----------------------------|--|------------|
| CML-CP | Progression to CML-AP or CML-BP at any time during the study Or WBC count that rises to $> 20.0 \times 10^9 / L$ ($> 20,000 / mm^3$) on two occasions at least 2 weeks apart (after first 4 weeks of K0706 therapy) in a subject Or | [REDACTED] |

| | | |
|---------------|--|------------|
| | Platelet count that rises to $> 600 \times 10^9/L$ ($> 600,000/mm^3$) on two occasions at least 2 weeks apart (after first 4 weeks of K0706 therapy) in a subject Or Loss of CHR (in the absence of a CyR) confirmed by complete blood counts done 4 weeks apart Or Loss of MCyR Or Death | |
| CML-AP | Development of confirmed BP Or Loss of previous major haematological response over a 2 week period Or No decrease from baseline levels in percentage blasts in peripheral blood or bone marrow on all assessments over a 4 week period (monitored at least every week) Or Death | [REDACTED] |
| CML-BP | Increasing blasts in peripheral blood or bone marrow over a 4 week period (monitored at least every week) Or Death | [REDACTED] |

Note: For subjects wherein rapid disease progression is observed (beyond the aforementioned criteria) and subject safety is a concern, the subject can be discontinued at Investigator's discretion

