7.5.2.4 Hematologic Response

A hematological response is a normalization of the blood counts, particularly WBC counts. This is the first noticeable indicator that treatment is beginning to work, though not necessarily in the bone marrow. The response can be a partial hematological response (reduction in WBC, but not down to normal range) or CHR.

The CHR will be evaluated by peripheral blood utilizing local laboratory results.

A CHR is usually anticipated within [REDACTED] of treatment, however, some subjects may take longer to achieve this level. The [REDACTED]
[REDACTED]

Refer to Appendix I and Operations Manual for the definitions of CHR and MaHR.

Sample logistics and the location of testing will be detailed in the Operational Manual.

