13 APPENDIX

13.1 APPENDIX I

CRITERIA FOR RESPONSE

Haematological response

Major haematological response (MaHR) is inclusive of complete haematological response (CHR) and/or no evidence of leukemia (NEL).

For subjects who enter the study in MaHR response, the criteria for evaluating response is: Maintenance of MaHR for upto 12 weeks after initiation of study treatment.

These criteria are adapted from Talpaz et al., 2006, O'Brien et al., 2003, and Kantarjian et al., 2010.

| Haematological response criteria for Subjects with CML-AP and CML-BP and Ph+ ALL | |
|--|---|
| CHR | 
 • White blood cells (WBCs) \leq Institutional upper limit of normal • $ANC \geq 1000/mm^3$ • Platelets $\geq 100,000/m^3$ • No blasts or promyelocytes in peripheral blood • $< 5\%$ basophils on differential • $< 5\%$ myelocytes and metamyelocytes on peripheral blood • No extra-medullary involvement (no hepatomegaly and/or splenomegaly) |
| NEL | 
White blood cells (WBCs) \leq Institutional upper limit of normal
 
No blasts or promyelocytes in peripheral blood
 
$< 5\%$ basophils on differential
 
$< 5\%$ myelocytes and metamyelocytes on peripheral blood
 
No extra-medullary involvement (no hepatomegaly and/or splenomegaly)
 
At least one of the following
 
 • $20,000/mm^3 \leq Platelets \leq 100,000/mm^3$ • $500/mm^3 \leq ANC \leq 1000/mm^3$ |

| Complete haematological response (CHR) for Subjects with CML-CP | |
|---|--|
| CHR | 
Platelets $< 450 \times 10^9/mm^3$
 
White blood cells (WBCs) \leq Institutional upper limit of normal
 
No blasts or promyelocytes in peripheral blood
 
$< 5\%$ basophils on differential
 |

| | |
|--|---|
| | < 5 % myelocytes and metamyelocytes on peripheral blood No extra-medullary involvement (no hepatomegaly and/or splenomegaly) |
|--|---|

Cytogenetic response:

Criteria for Cytogenetic response have been derived from Kantarjian et al, 2006, Talpaz et al, 2006 and National Comprehensive Cancer Network (NCCN), Clinical practice guidelines (2018).

At least 20 metaphase should be evaluated. If fewer metaphases are reported, absolute percentage values should be reported. Peripheral blood cells must not be used.

| Major Response | Cytogenetic Response | Complete (CCyR) | No Ph+ Cells |
|------------------|----------------------|-------------------------|--------------------|
| | | Partial Response (PCyR) | 1-35 % Ph+ Cells |

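### As printed, the CML-CP platelet limit for complete hematologic response is a million times too high, so that part of the definition cannot be failed

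*Protocol*

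**What the plan says.** Protocol Section 13.1 (Appendix I) lists the conditions for CHR in CML-CP, and the platelet condition is "Platelets $< 450 \times 10^9/mm^3". Three other places in the protocol show the scale on which platelets and white cells are counted:

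- Table 7-3 (Section 7.3.2.3) has progression criteria that pair the two units: "Platelet count that rises to $> 600 \times 10^9/L$ ($> 600,000/mm^3$) on two occasions at least 2 weeks apart" and "WBC count that rises to $> 20.0 \times 10^9 / L$ ($> 20,000 / mm^3$) on two occasions at least 2 weeks apart". Both apply after the first 4 weeks of treatment. Table 6-2 repeats them for Part B.
- Table 7-2 (Section 7.3.2.2) defines chronic phase partly by "> 100 \times 10^9$ platelets/L in peripheral blood".
- The NEL row of Appendix I uses "20,000/mm^3 \leq Platelets \leq 100,000/mm^3".

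CHR in CML-CP is used in two ways. Section 7.3.1.4.2 makes it a secondary endpoint: "Hematological responses: Proportion of subjects who achieve or maintain complete hematological response". Tables 6-2 and 7-3 make its loss a progression event: "Loss of CHR (in the absence of a CyR) confirmed by complete blood counts done 4 weeks apart". The efficacy paragraphs of the protocol summary take the response criteria for Parts B and C from Appendix I. Section 7.5.2.4 names two sources: "Refer to Appendix I and Operations Manual for the definitions of CHR and MaHR".

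**The concern.** A count in units of 10^9 belongs with litres, and a count per mm³ belongs with thousands. The Appendix I line joins the first scale to the second unit. The result is far above any platelet count, so the condition excludes nobody.

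This line is an endpoint threshold, not background text. If it is programmed or applied as printed, a chronic-phase subject with a raised platelet count who meets the other conditions is counted as a CHR, and that subject cannot later lose CHR because of platelets. CHR is read from local laboratory results, at about 90 planned centers for Parts B and C. If one site takes the line literally and another reads it as per litre, the same count would be classified differently.

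**Working it through.** **Inputs.** The printed limit of 450 × 10^9/mm³ is from Appendix I. The paired figures are from Table 7-3. The conversion is 1 L = 10^6 mm³.

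**Step 1: reproduce the protocol's own conversions.**
- White cells: 20.0 × 10^9/L ÷ 10^6 = 20,000/mm³, as stated.
- Platelets: 600 × 10^9/L ÷ 10^6 = 600,000/mm³, as stated.

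Both agree exactly, so the factor is the one the protocol itself uses.

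**Step 2: apply it to the Appendix I limit.**
- As printed: 450 × 10^9/mm³ × 10^6 = 4.5 × 10^17/L.
- On the Table 7-3 pattern: 450 × 10^9/L ÷ 10^6 = 450,000/mm³.
- Ratio of printed to consistent limit: 4.5 × 10^17 ÷ 4.5 × 10^11 = 10^6.
- Ratio of printed limit to the platelet progression cut-off: 450 × 10^9 ÷ 600,000 = 750,000.

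**Step 3: can the printed limit be reached?** One mm³ is 10^9 µm³, so a count at the limit leaves 10^9 ÷ (450 × 10^9) = 0.0022 µm³ per platelet. Assume a platelet volume of 1 to 15 fL (1 fL = 1 µm³; the range is an assumption, not taken from the documents). Solidly packed platelets would then number at most 10^9 ÷ 1 = 1 × 10^9/mm³ down to 10^9 ÷ 15 = 6.7 × 10^7/mm³. That is 0.22% to 0.015% of the limit, so no subject can fail it.

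**Step 4: what each rule does with a given count.**

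| Platelets per mm³ | Passes limit as printed | Passes < 450,000/mm³ | Above 600,000/mm³ |
|---|---|---|---|
| 300,000 | yes | yes | no |
| 450,000 | yes | no | no |
| 500,000 | yes | no | no |
| 600,000 | yes | no | no |
| 601,000 | yes | no | yes |
| 1,000,000 | yes | no | yes |

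For the CHR endpoint, every row from 450,000 upward is misclassified on platelets. The last row is 450,000 times below the printed limit (450 × 10^9 ÷ 1,000,000) but 2.2 times the consistent one (1,000,000 ÷ 450,000).

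For progression, the last two rows are still caught if the count is repeated at least 2 weeks apart after week 4. The rows from 450,000 to 600,000 are caught by neither platelet route. Even there, loss of CHR counts only when there is no cytogenetic response and the finding is confirmed 4 weeks apart.

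**The case against.** The strongest objection is that the fault may lie in the reading of the PDF. A limit of 450 × 10^3/mm³ would be correct and differs from the readable text by one superscript digit. The AP/BP CHR row of the same appendix gives its platelet floor per m³ where its neighbors use mm³, which may itself be an extraction fault. This stands as a reason to check the source page. It also means one cannot say whether the unit or the exponent is wrong. It does not change the intended value, because both corrections give 450,000/mm³.

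Second, a reader might infer that progression-free survival ignores thrombocytosis. The documents do not support that. Table 7-3 has its own platelet criterion, independent of CHR. SAP Section 13 also counts only progression that leads to withdrawal of the subject, or death.

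Third, a reader might infer that the main result or the SAP tables are affected. The Cohort A primary endpoint is major cytogenetic response, so it is untouched. The readable SAP text before Section 13 limits the hematologic response summary to AP and BP, so no visible SAP table uses this threshold. That is a separate conflict with the protocol's CML-CP endpoint and does not remove the endpoint. The SAP's hematologic criteria are redacted, so nothing shows that they repeat the figure.

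Fourth, the Operations Manual, which is not among the documents, may state the limit correctly. The note under Table 7-13 that refers to the appendix is attached to Cohorts B and C and says nothing about CML-CP. The link from CML-CP CHR to Appendix I rests on the protocol summary and Section 7.5.2.4.

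Finally, an experienced reader would probably take the line as per litre. That is likely, but an endpoint definition should not depend on it, and no readable text makes the correction.

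**Conclusion.** The platelet limit is wrong as written, by a factor of 10^6 on the protocol's own conversions, and the platelet part of the CML-CP CHR definition excludes nobody. The exposure is the CML-CP CHR secondary endpoint and, more narrowly, the loss-of-CHR progression criterion. The progression gap is mainly sustained counts of about 450,000 to 600,000/mm³ in subjects with no cytogenetic response.

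That every count passes is a logical consequence of the printed text, not an expected misclassification rate. The documents give no platelet distribution from which to estimate one. The conclusion assumes that the readable text matches the source page, which cannot be fully confirmed here, and that neither the Operations Manual nor the redacted SAP text already carries a workable limit. The correction should be made, but it does not threaten the primary analysis.

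**What to change.** Check the Appendix I source page and the published criteria it cites. If they confirm the numeral 450, restate the CML-CP CHR platelet limit as < 450 × 10^9/L (450,000/mm³), giving both units as Table 7-3 does. Check the platelet unit in the AP/BP CHR row at the same time. Align the Operations Manual and, only if the redacted SAP criteria repeat the figure, the SAP derivation.

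The cost is one corrected cell in an appendix and a consistency check of two companion documents. No change to sample size, visits or data collection is needed. If any CML-CP response or progression calls have already been made from the printed text, they should be re-derived from the recorded platelet counts.

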7.5.2.2 Cytogenetic Response

Bone marrow aspirate samples will be sent for review of cytogenetics by [REDACTED]

[REDACTED]

[REDACTED]

[REDACTED]

[REDACTED]

For subjects who demonstrate complete cytogenetic response on two repeated assessments, bone marrow aspirate samples may be collected at 6 monthly intervals thereafter.

Standard cytogenetic methods will be used to determine the presence of the Ph+ and its presence (percentage) in the bone marrow. At least [REDACTED] cells in metaphase will be evaluated for karyotyping. [REDACTED]

Cytogenetic response is a response to treatment of CML that occurs in the bone marrow, rather than just in the blood. A cytogenetic response means any Ph+ chromosome reading obtained after K0706 administration interpreted as described below.

There are 3 levels of cytogenetic response:

1. Partial Cytogenetic Response (PCyR): This indicates that only 1 to 35% of the sample contains Ph+ metaphases
2. Complete Cytogenetic Response (CCyR): This indicates no Ph+ cells can be measured by either conventional or fluorescence in situ hybridization cytogenetic testing (though the PCR test may still be positive)
3. Major Cytogenetic Response (MCyR) is cytogenetic response inclusive of PCyR and CCyR

Sample logistics and the location of testing will be detailed in the Laboratory Manual.

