7.8.1 Primary and Secondary Target Variables

Primary Endpoints

- Cohort A: For CML subjects in CP at study entry: major cytogenetic response (MCyR), defined as complete cytogenetic response (CCyR) or partial cytogenetic response (PCyR). (CP subjects in CCyR are not eligible for this study)
For subjects entering the study in PCyR, achieving CCyR on the study drug will be considered as MCyR.
- Cohort B: For CML subjects in AP at study entry: major hematologic response (MaHR), defined as complete hematologic response (CHR) or no evidence of leukemia (NEL). (AP subjects in MaHR are not eligible for this study)
- Cohort C : For CML subjects in BP : MaHR, consisting of CHR
Or NEL. (BP subjects in MaHR are not eligible for this study)

Secondary Endpoints

- In subjects with CML-CP
 - Hematological responses: Proportion of subjects who develop complete hematological response
 - Cytogenetic responses: Proportion of subjects who develop CCyR
 - Molecular responses: Proportion of subjects who achieve MMR
- In subjects with CML-AP or CML-BP

- Cytogenetic responses: Proportion of subjects who achieve CCyR or PCyR,
- Molecular responses: Proportion of subjects who achieve MMR
- In all subjects: Safety and tolerability in terms of incidence and severity of treatment emergent AEs
- In all subjects: Time to response, duration of response, progression free survival and overall survival

Table 7-13 Efficacy Assessment of Primary End points

| | Cohort A | | Cohort B and C ^a |
|-------------------------------|---|--|---|
| Primary endpoint will include | Subjects entering the study with less than PCyR | Unconfirmed MCyR: That is detection of a complete or partial cytogenetic response on a single bone marrow aspirate will qualify as a response for determination of efficacy. | Confirmed MaHR: This includes demonstration of CHR or NEL confirmed by 2 hematological assessments performed at least 4 weeks apart. The hematological assessments will include a peripheral blood CBC and differential to qualify as a response. |
| | Subjects entering the study with PCyR | Unconfirmed CCyR: That is detection of Complete cytogenetic response on a single bone marrow aspirate will qualify as a response for determination of efficacy. | |

a: Criteria for responses are included in Appendix 1

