| Minor Response | | | 36-65 % Ph+ Cells |
| Minimal Response | | | 66-95 % Ph+ Cells |
| No Response | | | 96-100 % Ph+ Cells |

Under limited bone marrow aspirate availability precluding cytogenetic evaluation by Giemsa staining, FISH assay for evaluation of Ph+ Cells will be performed. A CcyR is reported for FISH when No Ph+ cells* are observed or fewer than 1 out of 200 nuclei BCR-ABL1-positive by FISH.

Major Molecular Response:

A major molecular response (MMR), is defined as a ratio of reverse transcribed transcript of BCR-ABL to ABL ≤ 0.1 % on the international scale (IS) (equivalent to 3 log reduction in transcript) (Baccarani et al., 2009).

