10 MEDICATIONS

Prior, concomitant, and post-therapies will be coded using the latest available version of the Anatomical Therapeutic Chemical (ATC) classification text from the World Health Organization Drug Dictionary (WHO DD) and summarized using safety analysis set. Surgical and medical procedures will be coded by primary system organ class (SOC) and preferred term (PT) according to MedDRA coding dictionary.

Prior therapy:

Prior therapies are therapies which started and stopped before the first dose of Vodobatinib. Any changes to prior medications (dose, regimen, etc.) during the study will be considered a new concomitant medication.

The number and percentage of subjects who received any prior including anti-neoplastic medications will be summarized by the dose group for the safety analysis set. The number and percentage of subjects who received any prior including anti-leukemic medications will be summarized by the dose group for the safety analysis set. The prior medications will be summarized for the lowest anatomical therapeutic classification (ATC) class and preferred name.

Concomitant therapies:

Concomitant therapies are defined as all interventions (medications and procedures) other than the study treatment administered to a subject coinciding with the study treatment period. Concomitant therapies include medications and medical procedures starting on or after the first dose of study treatment or starting prior to the first dose of study treatment and continuing after the first dose of study treatment. Concomitant medication will be summarized by the lowest ATC class and preferred name using frequency counts and percentages. Surgical and medical procedures will be summarized by SOC and PT. A listing will also be provided.

[REDACTED]

[REDACTED]

[REDACTED]

[REDACTED]

Hematological Response:

Hematological response is a normalization of the blood counts, particularly WBC counts and is evaluated by peripheral blood assessments and clinical assessments of extramedullary disease.

[REDACTED]

[REDACTED]

[REDACTED]

[REDACTED]

[REDACTED]

[REDACTED]

[REDACTED]

[REDACTED]

[REDACTED]

[REDACTED]

Cytogenetic Response:

Cytogenetic response is assessed by the ratio of number of Ph+ cells seen to the number of cells analyzed on Karyotyping done by the central laboratory. In cases where karyotyping was not performed then the central laboratory florescence in situ hybridization (FISH) results will be

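### On the visible text, one karyotype with fewer than 20 metaphases can establish the Cohort A primary response; the plan should say when such a sample counts

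*Protocol*

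**What the plan says.** Appendix I (Protocol 13.1) sets the target, "At least 20 metaphase should be evaluated", and then covers shortfalls: "If fewer metaphases are reported, absolute percentage values should be reported". The response table that follows is by percentage of Ph+ cells alone. It gives no lower limit on cells counted and no category for an inadequate sample.

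Protocol 7.5.2.2 (Part C) states a required number, but the figure before "cells in metaphase will be evaluated for karyotyping" is redacted, as is the text after it. The section continues: "A cytogenetic response means any Ph+ chromosome reading obtained after K0706 administration interpreted as described below". PCyR is described this way: "This indicates that only 1 to 35% of the sample contains Ph+ metaphases".

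The SAP's Cytogenetic Response paragraph (in the text after Section 10) gives the derivation: "Cytogenetic response is assessed by the ratio of number of Ph+ cells seen to the number of cells analyzed on Karyotyping". No minimum denominator is visible, and the text that follows this derivation is partly redacted.

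For Cohort A, Table 7-13 (Protocol 7.8.1) requires no confirmation. A complete or partial response, or a complete response for subjects who enter in PCyR, "on a single bone marrow aspirate will qualify as a response for determination of efficacy". Cohorts B and C need two assessments at least 4 weeks apart.

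FISH appears in two roles. As a replacement, Appendix I says "FISH assay for evaluation of Ph+ Cells will be performed" when limited aspirate rules out karyotyping, and the SAP uses FISH when no karyotype was done. As an addition, Protocol 7.7.2 plans marrow FISH in subjects who have reached CCyR. Repeating an inevaluable marrow is described for screening only (Protocol 7.3.1 and 7.7.2).

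**The concern.** Read together, these rules let a very small karyotype decide the primary endpoint. A 5-cell karyotype has been performed, so it does not trigger the FISH replacement. It yields a percentage, the percentage falls in a response band, and one such reading is enough.

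Subjects entering in PCyR are the most exposed. Their primary response is a single CCyR, and finding no Ph+ cell among a handful is weak evidence that none exist. In an open-label, single-arm cohort judged on a response rate, a few chance responders would move the estimate upwards. Because one response suffices and later aspirates do not cancel it, repeated sampling adds chances of a false response.

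**Working it through.** The plan states no figure for this point, so there is none to reproduce. The check is exact binomial.

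**Inputs from the documents:** target of 20 metaphases; PCyR 1–35% Ph+; CCyR no Ph+ cells; one aspirate suffices. **Assumptions:** the true Ph+ fraction p, the number of cells n, and independent sampling of cells.

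**Formulas**
- Chance CCyR reading: P(0 Ph+ cells) = (1 − p)^n.
- Chance MCyR reading: P(X ≤ k), X ~ Binomial(n, p), with k the largest whole number not above 0.35n.

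| n | true 10% Ph+: 0.9^n | k | true 60% Ph+: P(X ≤ k) |
|---|---|---|---|
| 3 | 72.9% | 1 | 35.2% |
| 5 | 59.0% | 1 | 8.7% |
| 10 | 34.9% | 3 | 5.5% |
| 15 | 20.6% | 5 | 3.4% |
| 20 | 12.2% | 7 | 2.1% |

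Example, n = 5 at 60%: 0.4^5 + 5 × 0.6 × 0.4^4 = 0.0102 + 0.0768 = 0.087.

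The 35% at n = 3 is partly an artefact of whole numbers, because 1 of 3 (33%) falls just under the cut. At n = 4 the figure is 0.4^4 + 4 × 0.6 × 0.4^3 = 0.0256 + 0.1536 = 18%.

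**What a zero count excludes.** The one-sided 95% upper bound is 1 − 0.05^(1/n): 45% for 0 of 5 and 13.9% for 0 of 20.

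**Repeated aspirates.** Assume four independent aspirates, all of the same size, and true 65% Ph+. The per-aspirate chance of an MCyR reading is 5.4% at 5 cells and 0.6% at 20. Over four, 1 − (1 − q)^4 gives 19.9% and 2.4%.

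**The other direction.** At true 30% Ph+, a genuine MCyR is missed when X > k: 47% of 5-cell samples (X ≥ 2) and 23% of 20-cell samples (X ≥ 8).

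**What a floor of 20 leaves.** At true 40% Ph+, a 20-cell sample still reads 35% or less 41.6% of the time. At true 10%, 0 of 19 occurs by chance in 0.9^19 = 13.5% of samples, against 12.2% for 0 of 20.

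**The case against.** The strongest objection is redaction. The metaphase count and adjoining text in Protocol 7.5.2.2 are blacked out, as is text after the SAP derivation. An evaluability rule would naturally sit there. A reader might infer that the plan has no such rule; the documents do not support that, and the point is limited to what is visible. What stands is that the Appendix I wording is unredacted and contains no such limit, so it would need aligning with any hidden rule.

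Second, Appendix I says only that the percentage is to be reported. It could mean giving a raw figure instead of a response category. That reading is possible for the sentence alone. But 7.5.2.2 counts any post-dose reading and the SAP classifies by the ratio, so the visible text as a whole lets the percentage decide.

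Third, a reader might infer that a chance CCyR goes unchecked. Protocol 7.7.2 does plan marrow FISH after CCyR, and 7.5.2.2 mentions FISH in defining CCyR. So the largest figures concern a reading for which a second test is already planned. What remains is that neither Table 7-13 nor the visible SAP lets that FISH result change the endpoint, and it does nothing for PCyR.

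Fourth, small samples also lose true responders. That is correct, as shown above. It is only a partial offset, since a missed response can be found on a later aspirate while a false one stands.

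**Conclusion.** The point holds in a limited form. On the visible rules, a karyotype below the protocol's own 20-metaphase minimum can by itself create a Cohort A primary response. The size is material at about 3 to 5 cells, and for CCyR in subjects entering in PCyR also at 10 (35% against 12% at 20 cells, true 10% Ph+). For MCyR it is modest by 10 cells (5.5% against 2.1%, true 60%) and small by 15 (3.4%).

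These are per-sample probabilities under assumed Ph+ fractions. The documents do not say how often fewer than 20 metaphases are obtained, so the effect on the cohort's response rate cannot be stated. A reader might infer an inflated type I error for Cohort A. That is not supported: the sample size, null rate and responder threshold are redacted, and Protocol 7.8 says formal testing will not be performed. Nor can it be said that small samples only add responders.

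**What to change.** In Appendix I and the SAP's cytogenetic response text, state for the Cohort A primary endpoint:

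- A karyotype with fewer than 20 metaphases establishes CCyR only if marrow FISH on the same sample meets Appendix I's existing criterion (no Ph+ cells, or fewer than 1 of 200 nuclei positive). This also settles how the FISH planned in 7.7.2 is used.
- Otherwise that assessment is not evaluable for response, whether CCyR or PCyR. No FISH cut-off for PCyR is visible, so none is brought in.
- The subject stays in the denominator, consistent with the all-dosed efficacy set (Protocol 7.8.3.2, SAP 5.4), and can still respond on a later evaluable aspirate.
- The rate counting every karyotype is reported as a sensitivity analysis.

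If the redacted text already sets a rule, align Appendix I with it instead.

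The cost is wording in two documents plus one extra summary; the FISH assay is already in the plan. The downside is that a few true responses may be lost from the primary rate, which the sensitivity analysis will show. The cut at 20 is conventional: it treats 19 and 20 cells differently although their error is similar, and it does not remove chance error near 35%.
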